#### 4. Study Procedures

- a. Study design, including the sequence and timing of study procedures (distinguish research procedures from those that are part of routine care).

**Study Overview:** This study will be a between-group (total completer N=100) evaluation of genotype and sex, and a within-subject evaluation of opioid dose-response. The study will be conducted over 5 days (4 nights) at the Behavioral Pharmacology Research Unit (BPRU) and a residential clinical research unit (CRU) (Figure 1). Day 1 will be an Admission day. Days 2-5 will consist of blinded study drug administration in the morning, 1 pain testing session, and self-report/physiological measures of drug effects for 6 hours post dosing. Participants will receive double-blind doses of oral hydromorphone (2mg, 4mg, 8mg) (99-102) or weight and color-matched placebo in a randomized, counter-balanced research design.

**Screening Visit:** Participants will complete a brief phone screen to determine initial eligibility and will be invited to complete an in-clinic screen. Participants will sign an informed consent form with a study staff member to begin the Screening visit. To reduce expectancy effects, the consent will inform participants the study drug may consist of one or more of numerous different drug classes (e.g., opioids, stimulants, over-the-counter medications), a common practice in laboratory based studies of drug effects (103, 104). Following consent, a staff member will administer a battery of measures to establish study eligibility (see Study Measures below). A urine sample will be collected and tested for evidence of illicit drugs and to establish medical eligibility. A blood sample of no more than 2 tablespoons will also be collected from eligible participants for medical and genotype analysis. Participants will also be asked to provide a second blood sample (2 additional tablespoons) that will be collected at either Screening or Admission and stored for future genetic analysis. This will be voluntary. Participants who meet eligibility criteria (including results of laboratory blood tests) will be scheduled for an Admission day.

**Study Day 1, Admission Visit:** Participants will complete a brief history and physical to determine final study eligibility and will be admitted to the CRU for 5 days (Admission day + 4 session days). During the Admission day, participants will be familiarized with the pain testing procedures and the measures used during session days 2-5.

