## 6. Drugs/ Substances/ Devices

- a. The rationale for choosing the drug and dose or for choosing the device to be used.

We will administer oral hydromorphone in this study. We have selected hydromorphone because it is a prototypic, selective, potent, full MOR agonist that is frequently used in abuse liability studies as a surrogate for heroin, it is not subject to P450 metabolism, it has good oral bioavailability, there are no apparent sex effects of metabolism, it is used clinically for the treatment of pain, there is a wealth of literature available to which our research findings can be compared and interpreted, and we have several years experience administering it under double-blind, laboratory conditions (4, 7, 8, 128-135). The doses of hydromorphone chosen for this study are supported by a study conducted by Walsh et al., (2008), in which oral hydromorphone was administered to non-dependent individuals in doses up to 25mg (136). The authors of that study had no instances of respiratory depression or reductions in SpO2 at any of the doses administered. That study compared the reinforcing effects of oral hydromorphone with the two prominently abused opioid agonists hydrocodone and oxycodone within healthy volunteers who had a history of recreational opioid use but were not opioid dependent. Prior to beginning the study, the researchers conducted a pilot study wherein 5 doses of oral hydromorphone [2.5 mg – 35mg] were administered to enable identification of several safe, tolerable and detectable doses for study administration. The researchers reported the 2 lowest doses [2 and 5mg] were inactive within a population of recreational but non-dependent individuals, and ultimately selected three mid-range doses [10mg, 17.5mg, 25mg] based upon evidence of safety and tolerability.

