We have chosen to deliver doses lower than those administered by that study so we may evaluate whether there are individual differences in the ability to detect the low dose of hydromorphone. Participants in our study will receive three active hydromorphone doses. The first dose participants will receive is the mid-level dose, which will be administered on study Day 2. Any participant who has a negative reaction to this dose will be discharged from the study. The participants will receive placebo, low, and high doses on Days 3-5 of the study; the order of doses will be randomized and counter-balanced. These doses were deemed safe in the same participant population in the Walsh study, they produced a documented detectable range of subjective effects, and they represent suprathreshold doses consistent with those abused recreationally. Ultimately, we feel confident these dose values do not impose any unique risk above and beyond that presented by the administration of hydromorphone.

Generic powdered hydromorphone will be encapsulated using size 0, opaque, hard gelatin capsules; placebo will be size and weight matched and will contain microcrystalline cellulose filler. A pharmacy member with no participant interaction will conduct the dose randomization. All medication administration will be supervised and a medical staff member will be available to address any adverse events or to break the medication blind.

- b. Justification and safety information if FDA approved drugs will be administered for non-FDA approved indications or if doses or routes of administration or participant populations are changed.

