**Power and Correction for Multiple Testing:** Power (1-Type II error) and correction for multiple testing (control of Type I error) are important considerations in any genetic association study. Typically investigators attempt to control the Type I error rate of a given set of hypothesis tests by controlling the family wise error rate through manipulation of the alpha level of the test. This is not problematic when a handful of tests are performed at an alpha level (false positive level) of 5%, where the usual approach is the Bonferroni correction. We anticipate performing tests across multiple time-points and must adjust our target alpha level. Importantly, our 71 selected SNPs across the OPRM1 gene (see below) do not represent 71 independent tests due to correlation between SNPs. We will use an approach, termed SNPSpD (138) which uses spectral decomposition to estimate the number of independent tests across the region. Using available HapMap data, we estimate 44 independent tests across the region. We calculate power for the GLM approach modeling the effect of genotype on phenotype. If we assume a constant effect size difference between genotype groups (at each dose other than placebo), at an alpha level conservatively adjusted for 50 tests to .001, using the entire completer sample (N= 100) or the sex subsamples (N=50), we have >80% power for modest effect sizes of ~.45 and .67 respectively. In our calculations, effect size (Cohen's d) is the mean difference between genotype groups in standard deviation units. Importantly, this effect size is well within the range seen by other studies examining drug response difference in OPRM1 (e.g., Ray et al., 2004: effect size = 1.2).

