Protection Against Hydromorphone Risks: We also have extensive experience in the administration of hydromorphone and other opioid agonists in controlled laboratory settings and therefore anticipate few problems. Any individual who may be prone to the risks associated with hydromorphone will be excluded from participating. The FDA has identified the following conditions as increasing the risk for respiratory depression or other serious side effects following hydromorphone administration: patients with status asthmaticus; chronic obstructive pulmonary disease; reduced respiratory function; high blood pressure; impairment of hepatic, pulmonary or renal functions; myxedema or hyperthyroidism; adrenocortical insufficiency; gall bladder disease; acute alcoholism; history of convulsive disorders; history of head injury; currently taking sedatives, hypnotics or phenothiazines; and sulfite allergy. Mean exposure to hydromorphone is also increased 4-fold among patients with hepatic impairment and 3-fold among patients with renal impairment. Therefore, to further reduce the risk serious side effects, we will exclude any potential participant who exhibits one or more of these conditions. Second, although research staff and participants will be blinded to the exact medication provided, both groups will be informed of the potential side effects and risks associated with the study drug administration. Third, participants will be free to discontinue study participation at any time without consequence. Great care has been taken in selecting the appropriate drug doses to ensure hydromorphone is well-tolerated and safe for our participants. Fourth, standard concomitant medications (e.g., anti-nausea medications) will also be available as needed to treat any unpleasant side effects that may occur as a result of hydromorphone administration and participants will also be able to discontinue study participation at any time. Finally, the most serious risk associated with hydromorphone administration is respiratory depression. We believe this risk is minimal in this study for several reasons. First, we have selected a range of equipotent doses that we have previously demonstrated to be safe and well-tolerated in the same participant population (non opioid dependent individuals) (99-102) and based upon a previous study that piloted and ultimately administered identical doses to an identical research sample (136). Second, we have developed several standard criteria that are followed by nursing staff and research personnel to monitor participants who have been provided with a study medication. All nursing and research staff are informed of these standards, and a list of these standards is posted in each testing room. The standards are as follows: If respiratory rate drops below 8 breaths/minute and is accompanied by sedation, participants are prompted verbally to breath. In our experience, verbal and physical stimulation is often sufficient to prompt breathing and restore a normal respiratory rate. If respiratory rate drops further and/or if oxygen saturation rates fall below 90% saturation, successive dosing is terminated. Patients are monitored carefully with a “watch and wait” approach; during this period they are accompanied continuously by a medical and/or nursing staff member, evaluated by a staff physician, and are given supplemental oxygen at 2L/min via a nasal cannula (available on site in the exam testing room). If clinical evaluation determines that a participant’s sedation level is increasing, the opioid antagonist naloxone can be promptly administered via intramuscular route to produce an immediate reversal of opioid effects. There have been very few incidents throughout our >15 year experience administering opioid agonists to human participants in controlled laboratory conditions that have necessitated actual intervention (oxygen and/or naloxone), however our equipment and medical/nursing staff is always prepared for this possibility. We feel these procedures will sufficiently protect participants from possible adverse and serious adverse events. Finally, we will submit an annual review of study-related adverse and serious adverse events to the Johns Hopkins IRB and an independent group of consultants who will serve as our data safety monitoring board for evaluation.

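### The dose rationale contradicts itself on whether the planned doses match the cited study and are active, and the power statement assumes an equal genotype effect at every active dose without support

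*Combined protocol and SAP*

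**What the plan says.** Study Overview (Section 4a): "Participants will receive double-blind doses of oral hydromorphone (2mg, 4mg, 8mg) (99-102) or weight and color-matched placebo".

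Section 6a describes the cited oral hydromorphone study. On its pilot: "The researchers reported the 2 lowest doses [2 and 5mg] were inactive within a population of recreational but non-dependent individuals". On its main study, the researchers "ultimately selected three mid-range doses [10mg, 17.5mg, 25mg] based upon evidence of safety and tolerability". Section 6a then says that this trial deliberately goes lower, to look for individual differences in detecting the low dose. Later in the same paragraph it says that these doses were found safe in that study, and that "they produced a documented detectable range of subjective effects, and they represent suprathreshold doses consistent with those abused recreationally".

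Section 8b, on protection against hydromorphone risks, relies on the same study as one that piloted and "ultimately administered identical doses to an identical research sample (136").

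The power paragraph of Section 7c begins: "If we assume a constant effect size difference between genotype groups (at each dose other than placebo"). It claims more than 80% power at alpha .001 for d of about .45 with 100 completers and .67 with 50 per sex. The Association Model paragraph of 7c says the model can be extended to a two-way ANOVA over three doses. It names no genotype-by-dose term and no dose-specific contrast.

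**The concern.** There are two linked problems.

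The first is evidential. The planned doses are described as lower than the cited study's, as identical to them, and as suprathreshold with documented effects. The study cited for this is reported to have found doses in the same low range inactive. A reader relying on Sections 6a and 8b would be misinformed about where the evidence for activity and safety comes from.

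The second is statistical. The power claim needs the full genotype difference at each of 2, 4 and 8 mg. If a dose produces little response, ratings of high and liking may sit near the floor and leave little room for genotype groups to differ. A test that pools the doses would then be diluted. Section 7c gives no dose-by-dose evidence; its only benchmark is a single effect size of 1.2 from another study.

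**Working it through.** **1. The texts side by side**

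| Planned dose | What Section 6a's account of the cited study implies |
|---|---|
| 2 mg | named as inactive |
| 4 mg | lies between 2 and 5 mg, both reported inactive (inference by bracketing) |
| 8 mg | lies between 5 mg (inactive) and 10 mg (taken forward): neither supported nor contradicted |

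None of the three is among 10, 17.5 and 25 mg, so lower is consistent with the figures and identical is not. Section 6a also gives the pilot range as starting at 2.5 mg and then its lowest dose as 2 mg.

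**2. Inputs**

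From Section 7c: N = 100 (50 per sex), alpha = .05/50 = .001, d = .45 (.67), effect in SD units, so SD = 1. From Section 4a: three active doses.

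Assumed, because the plan does not state them: a 50:50 genotype split, two-sided testing, and an equal correlation r between a person's doses of 0, or .3 to .7.

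**3. Reproducing the plan's figure**

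Averaging three doses gives SD s = √((1+2r)/3). With r = 0 and a one-sided normal approximation (critical value 3.090):

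- N = 100: √3 × .45/√(1/50+1/50) = 3.897; 3.897 − 3.090 = .807, power 79.0%.
- N = 50: √3 × .67/√(1/25+1/25) = 4.103; 4.103 − 3.090 = 1.013, power 84.4%.

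This is the closest match on the stated Cohen's d scale. It treats a person's three doses as independent and puts the full effect at each. Two-sided, the same calculation gives 72.8% and 79.2%.

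**4. Varying the number of doses that carry the effect**

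Let m of the three doses carry d and the others none. The mean effect is d × m/3. With N = 100 the noncentrality is (.45 × m/3)/(0.2 × s), and the two-sided critical t on 98 df at .001 is 3.393. Noncentrality and power (noncentral t):

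| Effect present at | Mean d | r = 0 (s = .577) | r = .3 (s = .730) | r = .7 (s = .894) |
|---|---|---|---|---|
| all three doses | .45 | 3.90: 69% | 3.08: 38% | 2.52: 20% |
| two doses (one null) | .30 | 2.60: 22% | 2.05: 10% | 1.68: 5% |
| one dose (two null) | .15 | 1.30: 2% | 1.03: 1% | 0.84: 1% |

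A test at one dose alone has noncentrality .45/0.2 = 2.25 and power of about 14%.

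In the favourable variant of step 3 (one-sided, r = 0), power falls from 79.0% to 31.1% to 3.7% for N = 100, and from 84.4% to 36.1% to 4.2% for N = 50.

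**5. A contrast against placebo at one dose**

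The difference has SD √(2(1−r)). Assuming no genotype effect under placebo, the noncentrality at d = .45 is .45/(0.2 × SD):

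- r = .3: SD 1.183, noncentrality 1.90, power 7%.
- r = .5: SD 1, noncentrality 2.25, power 14%.
- r = .7: SD .775, noncentrality 2.90, power 32%.

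Splitting .001 over three such contrasts lowers these to 4%, 8% and 22%.

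**The case against.** Several points on the other side are sound.

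- **Inactive on average does not mean no genotype difference.** Section 6a chose low doses to study who can detect them, and a difference between genotypes near threshold is what that design looks for. The equal-effect assumption is therefore not disproved, and Section 7c presents it openly as an assumption. That same rationale does, however, suggest an effect that varies with dose, and nothing in the plan supports a constant one.
- **The plan does not commit to averaging over doses.** The two-way ANOVA can carry a genotype-by-dose term. Dilution is a risk of one possible analysis, not a property of the plan. What is missing is the choice of test and power for it.
- **Safety.** A reader might infer that the planned doses have no safety support. The documents do not say that. Section 6a reports no respiratory depression at any administered dose, up to 25 mg, and Sections 8a and 8b also cite the group's own studies, which cannot be examined here. What stands is that the cited study is misdescribed and that its safety evidence comes from higher doses.
- **Scope.** Section 6a does not say which measures were inactive. Floor effects concern self-report most directly; the primary outcomes also include pupil diameter, blood pressure and pain threshold. Pain threshold under placebo does not depend on dose activity.
- **Where the loss comes from.** A reader might infer that near-complete power collapses only because of inactive doses. That needs a larger effect than the plan's. At d = .45 with correlated doses, power is already well below 80% with a constant effect.

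**Conclusion.** The concern holds in limited form. The descriptions of the doses in Sections 4a, 6a and 8b cannot all be true. As reported in this protocol, the cited study does not document activity at the doses given.

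The claim of more than 80% power depends on an equal effect at every active dose that no stated evidence supports. For N = 100 and d = .45, a dose-averaged test has 69% power if a person's doses are uncorrelated and 38 to 20% at correlations of .3 to .7. With one null dose this becomes 22%, and 10 to 5%. With two it becomes about 2%, and 1%.

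These figures assume a 50:50 split, two-sided alpha .001 and equal SD at each dose. Fewer carriers would lower them: at a 20% carrier share, the constant-effect 69% becomes 40%. The null-dose rows are illustrations. They do not show that 2 or 4 mg has no genotype effect, and the documents do not support concluding that the trial cannot detect one.

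**What to change.** Reconcile Sections 4a, 6a and 8b so that they give one account of the doses, of their relation to the cited study, and of which source supports activity and which supports safety. No dose is proposed here.

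In Section 7c:

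- Stop relying on a constant effect across doses.
- Name the genotype-by-dose term in the two-way model already planned, with genotype contrasts at each active dose against placebo, and count them in the multiplicity correction.
- Restate power at the plan's own effect sizes for a constant effect, one null dose and two null doses, giving the genotype split, sidedness and within-person correlation used.

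The cost is protocol and SAP wording with no new data collection. The stated power will be less favourable, and the added contrasts use alpha and are weak on their own at d = .45 (7 to 32% each at r = .3 to .7, before any split). They show where an effect lies; they do not restore 80% power.

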## 7. Study Statistics

a. Primary outcome variables. The primary outcome variables are self-reported ratings of drug high and liking, changes in pupil diameter and blood pressure, pain threshold on 2 laboratory measures of pain, and analgesic efficacy in response to laboratory-induced pain. We expect that individuals with the minor allele of the A118G SNP and other

tagging SNPs across the OPRM1 gene will find hydromorphone more reinforcing (e.g., higher self-report ratings of high and drug-liking) and exhibit greater opioid-induced physiological changes (e.g., pupil diameter, blood pressure). Research also suggests the OPRM1 gene may also confer greater sensitivity to the negative effects of opioids, which may be observed as measuring greater ratings of nausea. We also hypothesize the minor allele and other tagging SNPs across the OPRM1 gene will produce higher pain threshold on 2 laboratory measures of pain, and lower analgesic efficacy in response to laboratory induced pain.

**b. Secondary outcome variables.** Decreases in cortisol levels as a function of the degree of pleasant effects of hydromorphone and painful stimuli, delay-discounting curves, and the effect of sex on all outcome measures. We hypothesize that individuals with the minor alleles will have greater decreases in cortisol levels as a function of the degree of pleasant effects of hydromorphone, lower cortisol in response to painful stimuli, and steeper discounting curves on a delay-discounting task. Finally, although we expect that the A118G will be associated with these effects, we hypothesize that several of the additional OPRM1 tagging SNPs will contribute to effect magnitude.

**c. Statistical plan including sample size justification and interim data analysis:** The aims of the proposed study will explore the impact of genetic variation across the OPRM1 gene on hydromorphone response. There are specific steps we describe below to assure that we interrogate all known functional variation across the OPRM1 gene, adequately cover all other variation using appropriately selected tagging SNPs, prevent spurious associations due to population stratification by accounting for local ancestry, and properly control the Type I error rate.

**Association Model:** Our primary goal is to demonstrate the impact of SNP variation across OPRM1 on variability in response to hydromorphone across time and dose. Association analyses will be performed by modeling genotype at each SNP in a general linear model. In its simplest form this test, commonly termed the measured genotype analysis (137), models the influence of genotypic variation at a given locus on variation in the quantitative trait, essentially a one-way Analysis of Variance (ANOVA). This approach provides a distinct advantage in that it can easily be extended to a two-way ANOVA to model genotype effects across 3 different doses of drug. In addition, the flexibility of the GLM allows incorporation of ancestry covariates and environmental moderators or mediators. We will examine the impact of OPRM1 at each time-point in separate analyses and account for the multiple testing using LD-adjusted Bonferroni correction (see below).

**Power and Correction for Multiple Testing:** Power (1-Type II error) and correction for multiple testing (control of Type I error) are important considerations in any genetic association study. Typically investigators attempt to control the Type I error rate of a given set of hypothesis tests by controlling the family wise error rate through manipulation of the alpha level of the test. This is not problematic when a handful of tests are performed at an alpha level (false positive level) of 5%, where the usual approach is the Bonferroni correction. We anticipate performing tests across multiple time-points and must adjust our target alpha level. Importantly, our 71 selected SNPs across the OPRM1 gene (see below) do not represent 71 independent tests due to correlation between SNPs. We will use an approach, termed SNPSpD (138) which uses spectral decomposition to estimate the number of independent tests across the region. Using available HapMap data, we estimate 44 independent tests across the region. We calculate power for the GLM approach modeling the effect of genotype on phenotype. If we assume a constant effect size difference between genotype groups (at each dose other than placebo), at an alpha level conservatively adjusted for 50 tests to .001, using the entire completer sample (N= 100) or the sex subsamples (N=50), we have >80% power for modest effect sizes of ~.45 and .67 respectively. In our calculations, effect size (Cohen's d) is the mean difference between genotype groups in standard deviation units. Importantly, this effect size is well within the range seen by other studies examining drug response difference in OPRM1 (e.g., Ray et al., 2004: effect size = 1.2).

**SNP selection (for association testing and control of Local Ancestry):** SNPs will be genotyped across the OPRM1 region to allow us to test associations across the gene and account for genetic ancestry (ethnicity). Typing all available SNP markers across the candidate gene set is inefficient and not necessary since many will provide redundant information due to linkage disequilibrium (LD). A more cost-effective strategy is to select a subset of representative SNPs (tagSNPs) that are in strong LD (measured through pairwise  $r^2$ ) with other SNPs that are therefore not required for genotyping in order to capture the haplotypic diversity across the gene. We followed this approach across OPRM1 with the Tagger algorithm at an  $r^2$  value of 0.8 and a minor allele threshold of 0.05 (139). We force included all predicted functional variation with allele frequency > .03 to allow for secondary hypothesis testing across OPRM1 functional SNPs. We used the latest Data release 21 (CEU Sample) of HapMap (<http://www.hapmap.org>) in conjunction with the NCBI build 35/hg17 of gene and EST data at UCSC Genome Browser (<http://genome.ucsc.edu/cgi-bin/hgGateway>). Using this approach, we selected 71 SNPs across the OPRM1 region for association testing and control of local ancestry. In our approach, we will re-estimate local ancestry for

each SNP association, dropping the tested SNP from ancestry estimation. Our approach to accounting for population stratification is detailed below.

**SNP Quality Control:** Maximizing genotype accuracy is a key step in maximizing our ability to detect true genotype-phenotype relationships. We will perform the usual checks to ensure data precision. We will first test Hardy-Weinberg equilibrium (HWE) and eliminate markers that exhibit large deviations from expected genotype distribution. The rationale for this step is to eliminate markers that may exhibit systematic genotype error (e.g., excess failure of a particular allele due to allele loss). We do realize that minor deviations from HWE will be observed by chance when testing such a large number of markers. Thus, we will use a stringent criterion for dropping markers exhibiting Hardy-Weinberg disequilibrium ( $p < 0.001$ ). Additionally we will eliminate markers that exhibit a high level (>5%) of missing data. A high level of missing data is generally interpreted as an indicator of a poor quality marker. We will eliminate individuals with a high level (>5%) of missing genotypes as this is likely due to poor DNA quality.

**Population Stratification:** In the context of genetic association testing, population stratification refers to genetic differences between subpopulations. This is especially problematic in instances where the investigators are blind to the presence of stratification and/or the population substrata also differ phenotypically. In these cases, association analyses will be prone to generate spurious genotype-phenotype relationships. Previously, several methods, including genomic control (140) and STRUCTURE (141) were proposed to deal with this issue by either correcting the test statistic for the average level of stratification or a priori grouping of population subsets. At the onset of the GWAS era, the wealth of genome-wide data gave rise to additional approaches which rely on the correlation structure of genetic information to identify cryptic population structure. EIGENSTRAT (142) is an example of an approach that uses genomewide data to infer principal components of population membership. Recently, several investigators (143, 144) have noted that differences in global (genomewide) versus local (at a gene or LD block) ancestry exist, especially in admixed populations (e.g., African-American). This is particularly germane to our setting given: 1) the genetic ancestry of the ECA sample is a mix of European-Americans and African-Americans, 2) the focus on a relatively small number of genes, and 3) the lack of genome-wide SNP data. We will use an approach (WinPOP/LAMP; (144, 145) to estimate proportions of local ancestry at each tested gene and account for stratification based on those mixing proportions in subsequent GLM tests. In order to accomplish this we will densely tag OPRM1.

**Analysis of pain testing sessions:** We hypothesize that OPRM1 SNP variants will exhibit greater pressure pain thresholds, greater CPM efficiency, lower hydromorphone-related analgesia, and lower cortisol stress response than participants with the major allele, and that results will be positively correlated with response to self-report and physiologically-mediated hydromorphone drug effects collected during days 3-5. Pressure pain threshold will be estimated by averaging the results of the 2 administrations to radiobrachialis and quadriceps muscle groups. We will generate a CPM index for each participant [(mean pressure pain threshold during cold pressor)/(mean pressure pain threshold prior to cold pressor)] x 100 (90). These values will provide a quantitative measure of percent change in the test stimulus (i.e., pressure point threshold). Mixed effects regression models with a random intercept will be used to compare dependent variables (pressure pain threshold, DNIC threshold, DNIC index) as a function of within-subject drug effects (placebo vs. hydromorphone), and between-subject effects of OPRM1 SNP analysis will be conducted as specified in Aim 1. Gender, age, and race have been associated with response to pain and the CPM test (146-148). Gender will be evaluated using independent subgroup analyses and age and race will be included as covariates. Finally, subscale scores of self-report measures of pain and coping strategies will be compared between the two genotype groups using independent samples t-tests, and drug identification data will be compared using a chi-square for each drug condition. We expect that both experimental manipulations will induce pain in the minor and major allele groups, and that participants with the minor allele will demonstrate lower sensitivity to pain (e.g., greater pressure pain magnitudes), lower NRS ratings of pain, lower cortisol response to painful stimuli, and lower analgesic relief from hydromorphone compared to the major allele participants.

**d. Early stopping rules.** The safety of participants is a priority of BPRU. If a participant experiences a serious side effect that seems to be related to the study drug, s/he will be discontinued from the study. If clinically indicated the participant will be referred to the Johns Hopkins Bayview Medical Center (JHBMC) Emergency Department for further treatment. BPRU and the CRU have policies in place to ensure safety of all participants and staff, and some policies may lead to administrative discharge of a participant, and therefore, discontinuation from the study. Participants who do not abide by the BPRU policies and procedures, or who demonstrate behaviors abusive of staff or other participants may be discontinued from the study. Intercurrent illness or condition changing a participant risk may result in medical discharge from the study.

Stopping criteria for the study: In addition, an independent panel of consultants will be contracted for review of the risks-benefits ratio of the study. At mid-point during enrollment this panel will be provided with a report of adverse events and participant outcome data (subjective response to hydromorphone) by unlabeled sex groups (A vs. B). This information will be used to assess whether the risks reported are considered to be of unusual magnitude or frequency across any specific group, and to determine whether the study should be ended prematurely due to participant safety concerns or because a result has been unequivocally demonstrated. It is unlikely that such a small study would be interrupted because of a large rate of adverse events, particularly given the noninvasive administration method of the medication (i.e., oral) and our experience at administering this drug, however we will ensure that a qualified panel of reviewers makes this decision.

